2.1.4.2 Deaths

The deaths observation period are per the observation periods defined above.

- Death on-study during DBTP: deaths occurring during the double-blind on-study observation period,
- Death on-treatment during DBTP: deaths occurring during the double-blind TEAE period,
- Death on-study during OLTP: deaths occurring during the open-label on-study observation period,
- Death on-treatment during OLTP: deaths occurring during the open-label TEAE period,
- Death post-study: deaths occurring after the last planned protocol visit.

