6.2 DURATION OF STUDY PARTICIPATION

6.2.1 Duration of study participation for each patient

The study duration includes a run-in period of 4 weeks, a screening period of up to 3 weeks, a 12-week DBTP for efficacy, and 52-week OLTP for efficacy and safety assessment.

Thus, the study duration per patient is approximately 71 weeks (i.e., 18 months maximum) (up to 4 weeks of run-in period + up to 3 weeks screening + 12 weeks double-blind treatment + 52 weeks open-label treatment).

Patients, who experience ongoing SAEs or adverse events of special interest (AESI), at the prespecified study end date, should be followed until resolution, stabilization, or death and related data will be collected.

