6.2.2 Determination of end of clinical trial (all patients)

The end of the study per patient is the last protocol planned visit or the resolution/stabilization of all SAEs, and AESI, whichever comes last.

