9.2.1 Adverse events

- All AEs diagnosed by the Investigator, irrespective of the result of the adjudication for CV events, will be reported and described.
- All AEs will be coded to a "Lowest Level Term (LLT)", "Preferred Term (PT)", "High Level Term (HLT)", "High Level Group Term (HLGT)" and associated primary "System

Organ Class (SOC)" using the version of MedDRA (Medical Dictionary for Regulatory Activities) currently in effect at Sanofi at the time of the considered database lock.

- AEs of special interest (AESI) include events such as the following:
 - General allergic events (please refer to [Section 10.4.4.1](#) and [Section 10.6.2](#))
 - Local injection site reactions (using special e-CRF pages) (please refer to [Section 10.4.4.2](#) and [Section 10.6](#)).
 - Hemolytic anemia (using special e-CRF pages, see [Section 10.4.4.1](#), Appendix D).
 - Neurologic (including neurocognitive) adverse events (please refer to [Section 10.4.4.1](#) and Appendix D).
 - Ophthalmologic adverse events (using special e-CRF pages, see [Section 10.4.4.1](#) and Appendix D).
 - Skeletal muscle-related adverse events (using special e-CRF pages, see [Section 10.4.4.2](#)).
 - Asymptomatic or symptomatic overdose with IMP (see [Section 10.4.4.1](#), [Section 10.4.4.2](#), and Appendix D).
 - Pregnancy of female patient (including male patient's partner) (see [Section 10.4.4.1](#) and Appendix D).
 - ALT increase (see [Section 10.4.4](#) and [Section 10.4.5](#)).

Refer to [Section 10.4](#) and [Section 10.6](#) for details.

Adjudicated CV events include all CV AEs and CV procedures positively adjudicated (see [Section 10.6.3](#)) occurring from randomization until end of the study. The adjudication categories are the following:

- CHD death.
- Non-fatal MI.
- Fatal and non-fatal ischemic and/or hemorrhagic stroke.
- Unstable angina requiring hospitalization.
- Congestive heart failure requiring hospitalization.
- Ischemia-driven coronary revascularization procedure.

In addition, the classification of all deaths will occur.

Adverse event observation period:

- The AE observations are per the observation periods defined above.

Death observations period:

- The death observations are per the observation period defined above. In addition, “post-study” death includes all deaths reported after the end of the study (see definition of end of study period per patient in [Section 6.2.2](#)).

9.2.2 Laboratory safety variables,

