- The open-label RESIDUAL TREATMENT period: defined as the time from the day of last dose of open-label IMP injection +22 days up to the day of last dose of open-label IMP injection +70 days (10 weeks).
- The open-label POST-TREATMENT period: defined as the time starting the day after the end of the open-label TEAE period (i.e., 71 days after the day of last dose of open-label IMP injection).

Observation periods below will be analyzed at the first step analysis only.

- The alirocumab exposed TEAE period is defined as follows :
 - For alirocumab 150 mg Q4W group and alirocumab 150 mg Q2W group: The time from the first dose of double-blind IMP injection to the last dose of IMP injection (double-blind or open-label) + 70 days (10 weeks).

- For placebo Q2W group: The time from the first dose of open-label IMP injection to the last dose of open-label IMP injection + 70 days (10 weeks).

The alirocumab exposed TEAE period will include:

- The alirocumab exposed TREATMENT period: defined below:
 - For alirocumab 150 mg Q4W group and alirocumab 150 mg Q2W group: The time from the first dose of double-blind IMP injection to the last dose of IMP injection (double-blind or open-label) + 21 days.
 - For placebo Q2W group: The time from the first dose of open-label IMP injection to the last dose of open-label IMP injection + 21 days.
- The alirocumab exposed RESIDUAL TREATMENT period: defined below:
 - For alirocumab 150 mg Q4W group and alirocumab 150 mg Q2W group: The time from the day of last dose of IMP injection(double-blind or open-label) +22 days up to the day of last dose of IMP injection(double-blind or open-label) +70 days (10 weeks).
 - For placebo Q2W group: The time from the day of last dose of open-label IMP injection +22 days up to the day of last dose of open-label IMP injection +70 days (10 weeks).

The double-blind on-study observation period is defined as the time from the day of first dose of double-blind IMP injection until the last protocol planned double-blind visit of the patient. The last protocol planned double-blind visit is defined as the follow-up visit if done, or a maximum of 20 weeks after the randomization of the patient, for patients not proceeding into OLTP. For patients proceeding into OLTP, the last protocol planned double-blind visit is defined as the end of double-blind treatment period visit (Week 12).

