The open-label on-study observation period is defined as the time from the first open-label IMP injection until the last protocol planned open-label visit of the patient.

The alirocumab exposed on-study observation period is defined below:

- For alirocumab 150 mg Q4W group and alirocumab 150 mg Q2W group: The time from the day of first dose of double-blind IMP injection until the last protocol planned double-blind visit for patients not entering into the OLTP or the last protocol planned open-label visit for patients entering into the OLTP.
- For placebo Q2W group: The time from the first open-label IMP injection until the last protocol planned open-label visit of the patient.

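### The SAP cuts on-study and post-study deaths at the last planned visit and drops the protocol's extension to resolution or stabilization of SAEs and AESIs

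*SAP*

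**What the plan says.** **Protocol.** Section 6.2.2 sets the end of study for a patient: "The end of the study per patient is the last protocol planned visit or the resolution/stabilization of all SAEs, and AESI, whichever comes last". Section 6.2.1 says that patients with ongoing SAEs or AESIs at the planned end "should be followed until resolution, stabilization, or death and related data will be collected". Section 9.2.1 builds the death category on that date: a post-study "death includes all deaths reported after the end of the study", with a cross-reference to 6.2.2.

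**SAP.** Section 2.1.4 ends the open-label on-study period at a visit; it is "the time from the first open-label IMP injection until the last protocol planned open-label visit of the patient". The double-blind on-study period ends at the Week 12 visit for patients who enter the OLTP. For the others it ends at the follow-up visit if done, "or a maximum of 20 weeks after the randomization of the patient, for patients not proceeding into OLTP". Section 2.1.4.2 then gives "Death post-study: deaths occurring after the last planned protocol visit" and "Death on-treatment during OLTP: deaths occurring during the open-label TEAE period". None of these carries the SAE/AESI extension. Sections 1.5 and 1.6, where changes would be declared, both state that they do not apply.

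SAP 2.4.5.2 tabulates deaths as on-study, on-treatment and post-study, with no rule for a death that fits more than one category.

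**The concern.** The protocol deliberately keeps following patients whose serious events are still open, and it counts that follow-up as part of the study. The SAP closes the on-study period earlier. The deaths affected are fatal outcomes of SAEs that were still open when visits ended, which a safety reader would want to see as on-study deaths. Few deaths can be expected among about 159 patients, so moving a single one can visibly change a row of the table.

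A second question arises when the same definitions are read together. On-treatment runs to 70 days after the last dose, while post-study starts after the last planned visit. If the first window outlasts the second boundary, one death can be on-treatment and post-study at once, and absent from on-study.

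**Working it through.** **1. The definitions side by side.** Take a patient whose SAE is neither resolved nor stabilized at the last planned visit and who later dies of it.
- Protocol: the second arm of 6.2.2 has not been met before the death, so the study has not ended for this patient and the death is not post-study.
- SAP: the death falls after the last planned visit, so it is post-study and lies outside the on-study period.

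This holds whichever visit is taken as last. As an illustration, a death on Day 520 from such an SAE is post-study in the SAP even with a Week 72 visit (Day 505), and is not post-study in the protocol. If the SAE had stabilized by the last visit, the two documents agree.

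**2. Inputs for the window arithmetic.**
- Week *w* is Day 7*w* + 1 (Protocol 1.2): Week 10 = Day 71, Week 20 = Day 141, Week 60 = Day 421, Week 62 = Day 435, Week 64 = Day 449, Week 72 = Day 505.
- Last open-label dose: Week 60 on Q4W, Week 62 on up-titrated Q2W (Protocol 8.1.2).
- TEAE period: to last dose + 70 days (Protocol 9.2, SAP 2.1.4).
- Last planned visit: Week 64 ± 5 days (Protocol 10.1.4.10). The SAP adds an 8-week follow-up (1.1) with visits at Week 72 (2.1.4.3, 2.1.4.4).
- Permitted injection delay: up to 7 days (Protocol 8.1.2).

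**3. The plan's own figures.** For patients not entering the OLTP, the last planned double-blind dose is at Week 10: Day 71 + 70 = Day 141 = Week 20. This reproduces the SAP's 20-week limit, so the nominal overlap there is 0 days. The protocol's per-patient duration is 4 + 3 + 12 + 52 = 71 weeks, which leaves no room for a follow-up period.

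**4. Open-label overlap = TEAE end − last planned visit.** TEAE end is 421 + 70 = Day 491 (Q4W) or 435 + 70 = Day 505 (Q2W).

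| Last planned visit | Q4W | Up-titrated Q2W |
|---|---|---|
| Week 64, Day 449 | 491 − 449 = 42 days | 505 − 449 = 56 days |
| Week 64 visit 5 days early or late (Day 444 or 454) | 47 or 37 days | 61 or 51 days |
| Week 72, Day 505 | 0 days | 0 days |
| Week 72, last dose 7 days late | 0 days (TEAE end Day 498) | 512 − 505 = 7 days |

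**5. Where the overlap comes from.** The protocol has it too. With no SAE or AESI ongoing, its end of study is Week 64, while its TEAE period still runs to Day 491 or Day 505. Restoring 6.2.2 in the SAP would leave such a patient's 42 or 56 days untouched.

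**The case against.** The strongest reply is that the SAP is coherent on its own schedule. With a Week 72 visit as the end, the open-label windows nest, and the 20-week limit nests in the same way for patients who do not enter the OLTP. This stands for the overlap, which depends on which visit is last. It does not answer the dropped SAE/AESI arm. Nor does it settle the schedule: the SAP refers to the last visit planned by the protocol, and the protocol has no Week 72 visit.

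A fixed, visit-based cut-off can also be defended, because a window that closes at event resolution has a length that depends on outcome. That would be a legitimate choice if declared. Here the SAP departs from a protocol definition while declaring no change.

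The impact is small, and that stands in full. Safety summaries are descriptive, open-label results are shown for all patients together (SAP 2.4.5), and TEAEs leading to death are counted whatever the date of death (SAP 2.4.5.2).

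Stronger readings that a reader might infer are not supported:
- *The SAP's departure causes the double classification.* It does not (step 5).
- *On-study deaths will be undercounted.* They can be, but only if such a death occurs.
- *Deaths are lost.* No fatal TEAE is lost; it can only be placed in the wrong period.
- *Early stoppers have an overlap of about 65 days (70 − 5).* This treats the discontinuation visit as the last planned one, but Protocol 10.3.4 calls it unscheduled.

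**Conclusion.** The mismatch is real and minor. SAP 2.1.4 and 2.1.4.2 omit the SAE/AESI arm of the protocol's end of study without declaring it. A death from an SAE neither resolved nor stabilized at the last planned visit then sits in a different category from the one in Protocol 9.2.1, and the on-study row can be too low. The protocol gives no explicit definition of an on-study death; I read it as one that is not post-study.

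The overlap of on-treatment with post-study is a separate defect. It is 42 or 56 days for completers on nominal timing if Week 64 is the last planned visit, and nominally 0 if Week 72 is. The documents disagree on which applies. No efficacy result or inferential test is affected.

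**What to change.** - In SAP 2.1.4 and 2.1.4.2, end each patient's final on-study period at the Protocol 6.2.2 end of study. Keep the Week 12 split between double-blind and open-label for patients entering the OLTP.
- Define post-study deaths as those after that date **and** outside any TEAE period, and state that on-treatment deaths count as on-study. Both conditions are needed. Adding TEAE-period deaths to on-study without removing them from post-study would let one death appear in all three rows. For example, a Q4W completer with no ongoing SAE or AESI who dies on Day 470 becomes on-treatment and on-study only.
- Reconcile whether the last planned visit is Week 64 (protocol) or Week 72 (SAP), and use one answer in both documents.

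The cost is SAP wording plus a derived end-of-study date from the follow-up that Protocol 6.2.1 already requires. There is a small downside. SAP 2.5.3 plans no imputation of AE resolution dates, and neither document names a field for the stabilization date, so the SAP must state a rule for when that date is missing.

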2.1.4.3 Laboratory safety variables

Clinical laboratory data consists of blood analysis, including hematology, clinical chemistry, and urinalysis. Clinical laboratory values after conversion will be analyzed into standard international units. International units will be used in all listings and tables. Clinical laboratory values converted into conventional (US) units will be also available in the database. Analyses can be provided upon request.

Unless otherwise specified below, blood samples for clinical laboratories were to be collected during:

- Screening period at Visit 2 (Week -3)
- DBTP at Visit 4 (Week 0), Visit 10 (Week 12) /or permanent treatment discontinuation
- OLTP at Visit 13 (Week 24), Visit 16 (Week 36), Visit 19 (Week 48), and Visit 23 (Week 64) /or permanent treatment discontinuation

- Follow-up period (Visit 24 [Week 72]) in case of abnormality at Visit 23 (Week 64).

The laboratory parameters (excluding those considered as efficacy parameters) will be classified as follows:

- Hematology:
 - Red blood cells and platelets:
red blood cell count, hemoglobin, red blood cell distribution width (RDW), reticulocyte count, hematocrit, platelets, haptoglobin;
 - White blood cells:
white blood cell count, neutrophils, lymphocytes, monocytes, basophils, eosinophils.
- Clinical chemistry:
 - Metabolism: glucose, total protein, albumin, creatine phosphokinase;
 - Electrolytes: sodium, potassium, chloride, bicarbonate, calcium, phosphorus;
 - Renal function: creatinine, glomerular filtration rate (eGFR), urea nitrogen, blood uric acid;
 - Liver function (also measured during DBTP at Week 4 and Week 8, except gamma glutamyl transferases [GGT] and lactate dehydrogenase [LDH]):
ALT, aspartate aminotransferase (AST), alkaline phosphatase (ALP), GGT, total bilirubin, and in case of total bilirubin values above the normal range, must include direct and indirect bilirubin, LDH.
- Hepatitis screen:
anti-hepatitis-C antibody (at Week -3 and Week 64/or permanent treatment discontinuation).

Technical formulas are described in [Section 2.5.1](#).

2.1.4.4 Vital signs variables

Vital signs include Body weight, heart rate (HR), systolic and diastolic blood pressure (SBP and DBP) in sitting position.

Body weight was to be measured during:

- Screening period at Week -3
- DBTP at Week 0, Week 12/or permanent treatment discontinuation
- OLTP at Week 24, Week 36, Week 64/or permanent treatment discontinuation
- Follow-up period (Week 72).

HR and blood pressure were to be measured during:

- Run-in and Screening period at Week -7, Week -3, Week -1

- DBTP at Week 0, Week 2, Week 4, Week 6, Week 8, Week 10, Week 12/or permanent treatment discontinuation
- OLTP at Week 20, Week 24, Week 36, Week 48, Week 64/or permanent treatment discontinuation
- Follow-up period (Week 72).

Vital signs will be described following time windows as defined in [Section 2.5.4, Table 4](#).

2.1.4.5 *Electrocardiogram variables*

The ECG parameters will be recorded automatically by the device at the Investigator site during:

- Screening period at Week -3
- DBTP at Week 12/or permanent treatment discontinuation
- OLTP at Week 24, and Week 64/or permanent treatment discontinuation.

ECG assessments will be described as normal or abnormal.

2.1.5 *Other endpoints*

Other assessment endpoints listed below are defined using same definitions and rules as for calculated LDL-C, when applicable (see [Section 2.1.3.1](#)).

- The absolute change in HbA1c (%) from baseline (Week -3) to Week 12 (DBTP), Week 24 (OLTP), Week 36 (OLTP), Week 48 (OLTP), and Week 64 (OLTP): PCSA criteria for HbA1c will be also used (see Appendix A).
- The proportion of patients with 2 consecutives results, spaced out by at least 21 days, of calculated LDL-C <25 mg/dL (<0.65 mmol/L) [REDACTED] during each treatment period (double-blind and open-label) and the time to the first calculated LDL-C <25 mg/dL [REDACTED] for these patients within the relevant treatment period.
- Proportion of patients who are up-titrated to alirocumab 150 mg Q2W during the OLTP.

2.1.6 *Anti-alirocumab antibodies variables*

Anti-alirocumab antibodies (ADA) are assessed:

- At baseline (before the first IMP injection)
- During DBTP at Week 4, Week 12
- During OLTP at Week 24, Week 36, Week 48 and Week 64/or permanent treatment discontinuation
- During follow-up (Week 72).

ADA measurements will be assigned to similar analysis windows as defined for efficacy endpoints ([Table 2](#)), with an additional analysis window for the ADA follow-up measurement performed at Week 72.

The following variables will be described:

- ADA response (Positive or Negative).
For ADA positive:
 - Titer levels;
 - Neutralizing status (Positive or Negative).
- Pre-existing positive ADA defined as patients with positive ADA response at baseline with less than 4-fold increase in titer in the post-baseline period;

Treatment-emergent positive ADA response defined as:

1) Patients with no ADA positive response at baseline but with any positive response in the post-baseline period (for DBTP: up to follow-up visit for patients not proceeding into OLTP, up to first open-label IMP injection for patients proceeding into OLTP, [REDACTED])

or

2) Patients with a positive ADA response at baseline and at least a 4-fold increase in titer in the post-baseline period (for DBTP: up to follow-up visit for patients not proceeding into OLTP, up to first open-label IMP injection for patients proceeding into OLTP [REDACTED])

For treatment-emergent positive ADA, the following categories for ADA duration will be applied:

- A persistent positive response is a treatment-emergent ADA positive response detected in at least 2 consecutive post-baseline samples separated by at least a 12-week period;
- An indeterminate duration positive response is defined as ADA present only at the last sampling time point;
- A transient positive response is defined as any treatment-emergent positive ADA response that is neither considered persistent nor indeterminate.

2.1.7 Pharmacokinetic variables

Concentrations of total alirocumab, total and free PCSK9 in serum are assessed at baseline (Week 0), Week 4, Week 8, Week 10, and Week 12.

Pharmacokinetic variable is the total alirocumab concentration at each time point. Depending on the timing of the sample versus the previous injection, C_{trough} , C_{max} and $C_{\text{follow-up}}$ will be defined as follows:

- [REDACTED]
- [REDACTED]
- [REDACTED]
- [REDACTED]
- [REDACTED]

Alirocumab concentration and total and free PCSK9 concentration will be described following time windows as defined in [Section 2.5.4, Table 3](#).

2.1.8 Pharmacodynamic/genomics endpoints

- [REDACTED]

2.1.9 Quality-of-life endpoints

- [REDACTED]

2.1.10 Health economic endpoints

- [REDACTED]

2.2 DISPOSITION OF PATIENTS

This section describes patient disposition for both patient study status and the patient analysis populations.

Screened patients are defined as any patient who met the inclusion criteria and signed the informed consent.

Randomized patients consist of all patients, with a treatment kit number allocated and recorded in IRT database, and regardless of whether the treatment kit was used or not. Patients treated without being randomized or treated with a double-blind or open-label treatment kit before the randomization will not be considered as randomized and will not be included in any analysis population.

For patient study status, the total number of patients in each of the following categories will be presented in the clinical study report using a flowchart diagram or summary table:

The following categories will be displayed for first and second step analysis:

- Screened patients
- Screen failure patients and reasons for screen failure
- Non-randomized but treated patients, if any
- Randomized patients
- Randomized but not treated patients and reason for not being treated
- Randomized and treated patients
- Patients who completed the double-blind study treatment period (at least 10 weeks of exposure with double-blind treatment and Week 12 visit performed)
- Patients who did not complete the double-blind study treatment period (as per definition above)
- Main reason for permanent double-blind treatment discontinuation (as per eCRF end-of-treatment form)

For all categories of patients (except for the screened and nonrandomized categories) percentages will be calculated using the number of randomized patients as the denominator.

Reasons for treatment discontinuation will be supplied in tables giving numbers and percentages by treatment group.

All major deviations potentially impacting efficacy analyses, randomization and drug-dispensing irregularities, and other important deviations will be summarized in tables giving numbers and percentages of deviations by treatment group. These deviations are listed in the data review and surveillance plan.

Additionally, the following populations will be summarized by treatment group:

- Randomized population.
- Efficacy population: ITT and mITT populations
- Safety population
- Pharmacokinetics population
- Anti-alirocumab antibody population
- Open-label treatment population
- Alirocumab safety population

Definitions of the study populations above are provided in [Section 2.3](#)

